8.2.7.2. Cardiovascular Events

A summary of the number and percentage of subjects with cardiovascular events will be reported by treatment group and therapeutic phase.

A by-subject listing of all the data elements collected on the eCRF page will be presented for subjects who experience cardiovascular events.

8.2.7.3. Pancreatitis and Pancreatic Cancer

The number and percent of subjects with pancreatitis and pancreatic cancer will be reported by treatment group. A by-subject listing of all the data elements collected on pancreatitis event page of the eCRF will be presented for subjects who experienced pancreatitis and pancreatic cancer. This listing of the pancreatitis events will also include the adjudication results as determined by the independent pancreatitis adjudication committee.

8.2.7.4. Thyroid Adverse Events

The number and percent of subjects with thyroid AEs will be reported by treatment group. Additionally thyroid adverse events identified by a customized MedDRA query will be presented by treatment group.

A by-subject listing of all the data elements captured in the thyroid tumor eCRF page will be produced.

8.2.7.5. Gastrointestinal (GI) Events

A summary of the number and percentage of subjects with GI events (specifically, AEs coded to the MedDRA SOC of gastrointestinal disorders) will be reported by treatment

group and therapeutic phase (pre-, on-, or post-therapy). Also, summaries of on-therapy GI events that lead to withdrawal of active treatment, treatment-related and serious GI events (including those that do not necessarily lead to withdrawal of active treatment) will be presented separately by treatment group.

For each subject, the time to first occurrence of a GI event is calculated as the number of days between the randomization date and the date of onset of the first on-therapy GI event plus 1. Subjects who do not experience any GI events will be censored at the last dose date + 25 days. The median time to first occurrence of a GI event as well as the Kaplan-Meier probability of first occurrence of a GI event at various time points will be presented for each treatment group.

The prevalence of GI events will be reported and plotted by treatment group.

The number and percentage of subjects reporting nausea at each study week will be presented by treatment group. Each week will include those subjects with onset of nausea during that particular week and also those subjects with nausea that started during a previous week but has not resolved. The prevalence of nausea will also be plotted over time. Similar summaries and plots will be presented for subjects reporting events of diarrhea and also separately for subjects reporting events of vomiting. In addition, a combined summary and accompanying plot of the number and percentage of subjects reporting events of nausea and/or vomiting will be presented.

8.2.7.6. Systemic Allergic Reactions

Systemic allergic reactions are reported by the investigators on the eCRF. The number and percentage of subjects with suspected systemic allergic reactions will be presented by treatment group. In addition, the time to first occurrence of a systemic allergic reaction will be analyzed and presented in a manner identical to that described above for first occurrence of a GI event.

A summary of systemic allergic reactions based on Customized MedDRA Query (CMQ) list identified by GSK will also be presented. Analyses will be repeated for this data.

8.2.7.7. Liver Events

The number and percentage of subjects with liver events that have been identified by investigators on the liver events eCRF page will be presented by treatment group. Additionally, liver events identified by a customized MedDRA query will also be presented by treatment group. By-subject listings of all the data elements collected on the eCRF page will be presented for subjects who experience adverse liver events, as identified by the investigators.

8.2.7.8. Atrial Fibrillation/Flutter

The number and percentage of subjects with Atrial Fibrillation/Flutter events will be presented by treatment group for Atrial Fibrillation and Atrial Flutter. By-subject listings of all the data elements collected on the Atrial Fibrillation and Atrial Flutter event eCRF

page will be presented for subjects who experience atrial fibrillation/flutter events, as reported by the investigators.

8.2.7.9. Pneumonia

The number and percentage of subjects with Pneumonia events will be presented by treatment group for Pneumonia event reported by the investigator on the eCRF. Summary of Pneumonia events identified by a customized MedDRA query will also be provided. By-subject listings of all the data elements collected on the Pneumonia event eCRF page will be presented for subjects who experience pneumonia events, as reported by the investigators.

8.2.7.10. Diabetic Retinopathy

The number and percentage of subjects with diabetic retinopathy events will be presented by treatment group. A by-subject listing of all the data elements collected on the diabetic retinopathy eCRF page will be presented for subjects who experience diabetic retinopathy, as reported by the investigators.

8.2.7.11. Appendicitis

The preferred terms containing the word “appendicitis” will be identified as Appendicitis events. The number and percentage of subjects with appendicitis will be presented by treatment group and a by-subject listing will be presented.

8.2.7.12. Malignant Neoplasm

Malignant neoplasm will be captured in the AE eCRF pages. The number and percentages of subjects with malignant neoplasm identified by a customized MedDRA query will be presented by treatment group and a by-subject listing will be presented.

8.2.8. Pregnancies

A listing of subject pregnancies will be provided.

8.2.9. Clinical Laboratory Evaluations

Laboratory results that are beyond the limits of quantification will have the inequality sign dropped (<, ≤, >, or ≥) and the quantification limit will be used as the numeric result for summarization.

8.2.9.1. Chemistry, Hematology and Urinalysis

Laboratory parameters include the following tests: hematology, chemistry and urinalysis. Established or generally acknowledged methods, normal ranges, and quality control procedures will be supplied by central lab for the study records.

Hematology parameters used in summaries include complete blood count with red blood cell indices, white blood cell count with differential, and platelet count. Chemistry parameters (including lipids) used in summaries include blood urea nitrogen (BUN),

potassium, aspartate aminotransferase (AST), total and direct bilirubin, creatinine, sodium, ALT, total protein, calcium, chloride, alkaline phosphatase (ALP), albumin, bicarbonate, uric acid, gamma glutamyl transferase (GGT), estimated glomerular filtration rate (eGFR), and lipids (including total cholesterol, LDL-C, HDL C, triglycerides, free fatty acids). Urinalysis include specific gravity, pH, glucose, protein, blood and ketones by dipstick and microscopic examination (if blood or protein is abnormal). Note that white blood cell absolute count was not collected in the study.

All laboratory parameters will be summarized, for each treatment group, at every scheduled assessment time point using descriptive statistics and presented graphically. In addition, for hematology and chemistry laboratory parameters, change from Baseline in these quantitative tests will be summarized by treatment group and at every scheduled assessment postbaseline time point. Shift tables providing the number and percentage of subjects with indicated shifts (normal, abnormal not of clinical concern, abnormal of clinical concern) in their results from baseline to each scheduled postbaseline assessment will also be presented for all hematology and chemistry parameters.

Additionally, the number of subjects with laboratory values of potential clinical concern will be summarized by treatment group and scheduled assessment time point for hematology and chemistry. The criteria for laboratory values of potential clinical concern are detailed in [Appendix 7: Values of Potential Clinical Importance](#).

A summary of laboratory values of potential clinical concern will be provided for liver function tests, including ALT, AST, and total bilirubin. The criteria for liver function tests of potential clinical concern are detailed in [Appendix 7: Values of Potential Clinical Importance](#).

All summaries will be done for the safety population and all laboratory data will be listed including other laboratory tests, such as HIV, Lipase, Amylase, hepatitis B, hepatitis C, TSH, and urine pregnancy test results.

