8.2.10. Other Safety Measures

8.2.10.1. Vital Signs

The vital sign summary and analysis will include systolic blood pressure (mmHg), diastolic blood pressure (mmHg), and heart rate (bpm).

Each vital sign parameter at every scheduled assessment time point will be summarized using descriptive statistics and presented graphically. Change from Baseline will also be summarized using descriptive statistics and presented graphically. Additionally, the number of subjects with vital signs of potential clinical concern will also be summarized. Shift tables providing the number and percentage of subjects with indicated shifts (normal, low value of clinical concern, high value of clinical concern) in their results from baseline to each scheduled postbaseline assessment will also be presented. The criteria for vital signs of potential clinical concern are detailed in [Appendix 7: Values of Potential Clinical Importance](#).

All summaries will be done for the safety population and all vital sign data will be listed.

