11.7. Appendix 7: Values of Potential Clinical Importance

11.7.1. Laboratory

Hematology			
Laboratory Test	Units	Change from Baseline of Potential Clinical Concern	Potential Clinical Concern Value
Basophils	GI/L	None	None
Eosinophils	GI/L	None	None
Hematocrit	1	>0.1 decrease	>0.05 below LLN >0.04 above ULN
Hemoglobin	g/L	>25 g/L decrease	>20 g/L below LLN >10 g/L above ULN
Lymphocytes	GI/L	None	<0.5 x LLN
Monocytes	GI/L	None	None
Neutrophils	GI/L	None	<1 GI/L
Neutrophil Bands	GI/L	None	None
Platelets	GI/L	None	<80 GI/L >500 GI/L
Red Blood Cell Count	TI/L	None	None
Segmented Neutrophils	GI/L	None	<0.5 x LLN
White Blood Cell Count	GI/L	None	>1 GI/L below LLN >5 GI/L above ULN

Chemistry			
Laboratory Test	Units	Change from Baseline of Potential Clinical Concern	Potential Clinical Concern Value
Albumin	g/L	None	>5 g/L above ULN or below LLN
Alkaline Phosphatase	U/L	None	>3 x ULN
ALT	U/L	None	>3 x ULN
AST	U/L	None	>3 x ULN
Bicarbonate (Carbon Dioxide Content)	mmol/L	None	<16 mmol/L > 40 mmol/L
Blood Urea Nitrogen	mmol/L	None	>2 x ULN
Calcitonin	pmol/L	None	>100

Chemistry			
Laboratory Test	Units	Change from Baseline of Potential Clinical Concern	Potential Clinical Concern Value
Calcium	mmol/L	None	<1.8 mmol/L >3.0 mmol/L
Chloride	mmol/L	None	None
Creatinine	umol/L	None	>159 umol/L
Direct Bilirubin	umol/L	None	>1.35 x ULN
Gamma Glutamyl Transferase	U/L	None	>3 x ULN
Glucose (fasting)	mmol/L	None	<3 mmol/L >22 mmol/L
Potassium	mmol/L	None	>0.5 mmol/L below LLN >1.0 mmol/L above ULN
Sodium	mmol/L	None	>5 mmol/L above ULN or below LLN
Total Bilirubin	umol/L	None	>1.5 x ULN
Total Protein	g/L	None	>15 g/L above ULN or below LLN
Uric acid	umol/L	None	>654 umol/L
Free Fatty Acids	mmol/L	None	None
HDL Cholesterol	mmol/L	None	None
LDL Cholesterol	mmol/L	None	None
Triglycerides	mmol/L	None	> 9.04 mmol/L
Total Cholesterol	mmol/L	None	None

Liver Function Tests

Liver Function Tests	
Laboratory Test	Potential Clinical Concern Value
ALT	≥ 2 x ULN ≥ 3 x ULN ≥ 5 x ULN ≥ 8 x ULN ≥ 10 x ULN ≥ 3 x ULN and Total Bilirubin ≥ 2 x ULN
AST	≥ 2 x ULN ≥ 3 x ULN ≥ 5 x ULN ≥ 8 x ULN ≥ 10 x ULN ≥ 3 x ULN and Total Bilirubin ≥ 2 x ULN
Total Bilirubin	≥ 1.5 x ULN ≥ 2 x ULN ≥ 3 x ULN ≥ 5 x ULN ≥ 8 x ULN ≥ 10 x ULN

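### The laboratory shift tables in SAP 8.2.9.1 grade abnormal results by concern but not by direction, so newly low and newly high values share a cell

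*SAP*

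**What the plan says.** SAP 8.2.9.1 gives the laboratory shift categories as "normal, abnormal not of clinical concern, abnormal of clinical concern) in their results from baseline to each scheduled postbaseline assessment", and says that the tables "will also be presented for all hematology and chemistry parameters". That is one normal category and two abnormal grades, with no low or high label on either grade.

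SAP Appendix 7 (11.7.1) sets the concern limits behind the grades. Many are two-sided, for example:

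- calcium: "<1.8 mmol/L >3.0 mmol/L"
- potassium: ">0.5 mmol/L below LLN >1.0 mmol/L above ULN"
- sodium: ">5 mmol/L above ULN or below LLN"
- platelets: "<80 GI/L >500 GI/L"
- hemoglobin: ">20 g/L below LLN >10 g/L above ULN"

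The shift tables for vital signs (SAP 8.2.10.1) and ECG (SAP 8.2.10.2) use directional categories instead: "normal, low value of clinical concern, high value of clinical concern".

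In Appendix 14 the hematology and chemistry shift displays (Tables 3.226 and 3.227) appear by title only, with no shell or programming note that adds direction. The same is true of the by-visit tables of values of clinical concern (3.223 and 3.224).

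**The concern.** A shift table counts, by arm, how many subjects moved from one state to another. If the states carry no direction, a fall below the normal range and a rise above it enter the same count. Two arms could then show the same number of new abnormal values while one product tends to lower a test and the other to raise it.

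This has some weight here. Safety and tolerability of the new formulation are a secondary objective (Protocol Section 3), and Protocol 9.4.2 rules out inferential testing on safety variables, so the descriptive tables carry the comparison. Protocol Table 2 also notes that gastrointestinal events may cause dehydration and affect the kidneys, so the direction of an electrolyte change is informative.

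**Working it through.** The plan states no figure on this point, so there is none to reproduce. The check is two counts and some worked cases.

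**1. How many tests have two-sided concern limits?** Appendix 7 has 12 hematology and 23 chemistry rows, 35 in all. By the potential clinical concern value column:

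| | Low and high limit | One limit | No limit | Rows |
|---|---|---|---|---|
| Hematology | 4 | 3 | 5 | 12 |
| Chemistry | 7 | 11 | 5 | 23 |
| Total | 11 | 14 | 10 | 35 |

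The 11 are hematocrit, hemoglobin, platelets, white cell count, albumin, bicarbonate, calcium, fasting glucose, potassium, sodium and total protein. SAP 8.2.9.1 notes that the absolute white cell count was not collected, and its chemistry list does not contain glucose. Without these two, 11 − 2 = 9.

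**2. Which reversals are hidden?** For a test with two-sided limits there are five true states: low of concern, low, normal, high, high of concern. The plan maps them to three categories.

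- Low to high: 2 low states × 2 high states = 4. High to low: another 4. Total 8.
- Same grade before and after: low of concern to high of concern, low to high without concern, and the reverse of each = 4. These fall on the diagonal and read as no shift.
- The remaining 8 − 4 = 4 read as a change of grade. The change of direction is not visible.

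These are kinds of transition, not probabilities; the documents give no rates.

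**3. Worked cases from Appendix 7 limits.**

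- Calcium 1.7 to 3.1 mmol/L: 1.7 < 1.8 and 3.1 > 3.0, so it is of concern at both visits and tabulated as unchanged.
- Potassium 0.4 mmol/L below the lower limit of normal to 0.9 mmol/L above the upper limit: 0.4 does not exceed 0.5 and 0.9 does not exceed 1.0, so it is abnormal without concern at both visits and tabulated as unchanged.

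**4. New abnormal values.** Each normal-to-abnormal cell pools two opposite changes. If a proportion p of one arm becomes newly low and the same p of the other newly high, at the same grade, the table shows p against p for any p. As an assumed illustration, p = 3% of 150 subjects is 0.03 × 150 = 4.5, so about 4 or 5 subjects per arm would appear as balanced.

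**5. What the other planned displays offer.**

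| Display | Keeps direction? | Count by arm of subjects shifting low versus high? |
|---|---|---|
| Change from baseline by visit (Tables 3.221, 3.222) and graphs (Figures 3.31 to 3.34) | Yes, as group summaries | No |
| Listings 33, 34, 138, 139 | Yes, subject by subject | No |
| Values of concern by visit (Tables 3.223, 3.224) | Not stated | Not stated; they count values at a visit, not shifts |

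For chemistry, Appendix 7 lists no change-from-baseline concern criterion for any test, so the shift table is the only planned categorical count of within-subject chemistry change.

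**The case against.** The strongest reply is that this is a layout preference in a descriptive display. Direction is available elsewhere: change from baseline is summarized by arm and visit, and Protocol 9.4.2 asks for the minimum and maximum, so extremes on each side would be seen. Graphs show mean values and mean change, and listings show every result. A systematic drift up in one arm and down in the other would appear as mean changes of opposite sign. The named safety focus is immunogenicity and injection site reactions, not laboratory tests. The vital-sign and ECG tables made a different choice: they have direction but no grade for abnormal values without concern, whereas the laboratory tables use their categories for that grade. More categories also mean sparser tables with about 150 subjects per arm.

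Most of this stands and limits the size of the point. It does not remove it. Group means can cancel opposite individual changes, minimum and maximum are not counts, and listings leave the tally to the reader. The vital-sign and ECG tables are a precedent for direction, not proof of a contradiction.

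Four stronger readings might be inferred, and the documents do not support them:

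- That there is a single abnormal category, so every low-to-high swing disappears. There are two grades, and half of the possible reversals do register as a change of grade.
- That opposite values of concern share a cell for every test. With a one-sided limit, such as ALT or creatinine, the of-concern cell has one direction; only the lower abnormal grade can still mix low and high.
- That fasting glucose is a good example. It is not in the 8.2.9.1 chemistry list, it has its own efficacy analyses, and hypoglycemia is tabulated separately.
- That Tables 3.223 and 3.224 pool low and high. The SAP does not say whether they do.

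**Conclusion.** The point holds as a small, inexpensive improvement. It rests on the stated wording of SAP 8.2.9.1, not on missing detail: applied as written, the categories pool newly low with newly high values and show same-grade reversals as no shift. Pooling of opposite values of concern affects 9 to 11 of the 35 Appendix 7 rows, depending on whether white cell count and fasting glucose are counted. Full reversals are probably the rarer problem; the merging of new low and new high values in one cell is the more practical one.

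A reader should not conclude that laboratory direction is lost from the report, or that any endpoint, error rate or efficacy result is touched. What is missing is a count by arm of subjects shifting low versus high. The conclusion assumes that Tables 3.226 and 3.227 will be built from the text of 8.2.9.1, since no shell says otherwise.

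**What to change.** In SAP 8.2.9.1, define the laboratory shift categories as low of concern, low, normal, high and high of concern. Collapse them where Appendix 7 has one limit (four categories) or none (low, normal, high). State also that Tables 3.223 and 3.224 count low and high values of concern separately.

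The cost is SAP wording and table length. For a test with two-sided limits the grid grows from 3 × 3 = 9 to 5 × 5 = 25 cells per visit and arm; with one limit it is 4 × 4 = 16; with none it stays at 9. Many added cells will be sparse or empty. No new data are needed, because the central laboratory already supplies the normal ranges.

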8.2.10. Other Safety Measures

8.2.10.1. Vital Signs

The vital sign summary and analysis will include systolic blood pressure (mmHg), diastolic blood pressure (mmHg), and heart rate (bpm).

Each vital sign parameter at every scheduled assessment time point will be summarized using descriptive statistics and presented graphically. Change from Baseline will also be summarized using descriptive statistics and presented graphically. Additionally, the number of subjects with vital signs of potential clinical concern will also be summarized. Shift tables providing the number and percentage of subjects with indicated shifts (normal, low value of clinical concern, high value of clinical concern) in their results from baseline to each scheduled postbaseline assessment will also be presented. The criteria for vital signs of potential clinical concern are detailed in [Appendix 7: Values of Potential Clinical Importance](#).

All summaries will be done for the safety population and all vital sign data will be listed.

8.2.10.2. Electrocardiograms

ECG parameters collected at each scheduled assessment time point include heart rate, QRS interval, QT interval, QT interval – Bazett correction (QTcB), QT interval – Fridericia correction (QTcF), RR interval and PR interval.

Each ECG parameter at each scheduled assessment time point will be summarized by treatment group using descriptive statistics and presented graphically. Change from Baseline will also be summarized using descriptive statistics. A summary of the number and percentage of subjects in overall ECG interpretation and abnormal findings will be displayed by treatment group. The number of subjects with ECG values of potential clinical concern will also be summarized. Shift tables providing the number and percentage of subjects with indicated shifts (normal, low value of clinical concern, high value of clinical concern) in their results from baseline to each scheduled postbaseline assessment will also be presented. The criteria for ECG values of potential clinical concern are detailed in [Appendix 7: Values of Potential Clinical Importance](#).

Additional notable abnormality criteria are defined based on the corrected QT interval (both QTcB and QTcF values) as the following: >450 msec, >480 msec, >500 msec, >30 msec increase from baseline, and >60 msec increase from baseline. The numbers and percentages of subjects who have notable abnormalities at any time post-baseline will be presented overall and by treatment group.

All summaries will be done for the safety population and all ECG data will be listed.

8.2.10.3. Physical Exams

In this study, findings from physical exams will be recorded in the AE eCRF page or medical history CRF page by the investigator as deemed appropriate. No separate summary of physical exams will be provided.

8.3. Pharmacokinetic Analyses

Blood samples for the determination of albiglutide plasma concentrations will be obtained from all subjects before administration of study treatment at Week 12 and Week 26/early withdrawal. During visits where ECGs and vital sign measurements are required, blood samples will be collected after measurement of ECGs and vital signs.

Albiglutide concentrations will be summarized by treatment group at each visit using descriptive statistics (n, mean, SD, coefficient of variation [%], median, minimum, maximum, geometric mean and geometric mean coefficient of variation [%]).

Data will be summarized for the PK population and individual subject concentration data will be listed.

